6. Anticipated need for postoperative anticoagulation with coumadin, dabigatran or rivaroxaban (mechanical valve, chronic atrial fibrillation, DVT/PE)
7. History of gastrointestinal hemorrhage
8. Active pathological bleeding
9. History of intracranial hemorrhage

10. Severe hepatic impairment
11. Current or anticipated use of strong CYP3A4 inhibitors (e.g. ketoconazole, clarithromycin, nefazadone, ritonavir, and atazanavir)

Study Conduct

Restrictions during the Study

Patients who require long-term anticoagulation (chronic atrial fibrillation, mechanical valve) will not be recruited into the TARGET trial, due to the higher risk of bleeding complications associated with the combination of both ticagrelor and coumadin. Despite this exclusion, subjects who are recruited into the trial may subsequently develop an indication for anticoagulation after study enrollment. As an example, anticoagulation may be necessary starting 10 days after surgery for a TARGET participant who has developed new-onset postoperative atrial fibrillation or deep vein thrombosis. In this scenario, the trial subject will discontinue the blinded study medication (aspirin or ticagrelor) and receive open label treatment as indicated by the clinicians involved in the patient's care (i.e. open label 81 mg aspirin daily plus coumadin). When anticoagulation is no longer needed (resolved atrial fibrillation), or the course of coumadin has been completed, open label treatment will cease, and the trial subject will resume the blinded study medication. The subject will continue to be followed as part of the trial and undergo CT graft evaluation irrespective of study medication interruptions.

In the case of a serious bleeding event (i.e. gastrointestinal bleeding requiring hospitalization) while enrolled in TARGET, a study subject will permanently discontinue the study medication. The patient will continue to be followed for the duration of trial enrollment, but the subject will receive open label treatment as indicated by the clinicians involved in the patient's care (i.e. open label 81 mg aspirin daily).

Subject Enrollment and Randomization

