A recruited subject who subsequently develops an indication for anticoagulation (i.e. new-onset postoperative atrial fibrillation or deep vein thrombosis) will be asked to discontinue the TARGET blinded study medication. The participant will then receive open label treatment as indicated by the clinicians involved in the patient's care (i.e. open label 81 mg aspirin daily plus coumadin). When anticoagulation is no longer needed (resolved atrial fibrillation), or the course of coumadin has been completed, open label treatment will cease, and the trial subject will be asked to resume the blinded study medication.

In the case of a serious bleeding event (i.e. gastrointestinal bleeding requiring hospitalization) while enrolled in TARGET, a study subject will permanently discontinue the study medication.

Procedures for Discontinuation of a Subject from Investigational Drug

If it is determined that a patient will be discontinued from the investigational drug, then alternate medication will be prescribed, if applicable, by the Principal Investigator or the patient's health care provider. Attempts will be made to obtain any remaining investigational drug in the patient's possession.

Withdrawal from Study

A patient may be withdrawn from study medication at any time by the study doctor or the sponsor without the patient's consent. For example: if it is in the patient's best interest, if the patient has problems complying with study procedures, if the patient becomes pregnant, if the patient does not consent to continue in the study after being told of changes in the research, if the patient makes a request, if the patient has a serious adverse event (GI bleed), or for any other reason.

Collection of Study Variables

Recording of Data

Case report forms will be designed and utilized to collect all pertinent data.

Data Collection at Enrollment and Follow-up

Saphenous vein graft patency and stenosis will be assessed by CT coronary angiography at 1 year and 2 years after CABG. The incidence of major adverse coronary events and safety outcomes will be documented during postoperative visit at 1 month after surgery and every 3 months thereafter. A research coordinator will phone each patient every 3 months to document any other events and ensure study drug compliance. This data will be recorded on the case report forms.

Enrollment Procedures

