Unlikely related – no temporal association, or the cause of the event has been identified, or the drug, biological or device cannot be implicated

Possibly related – temporal association, but other etiologies are likely to be the cause; however involvement of the drug, biological, or device cannot be excluded

Probably related – temporal association and other etiologies are possible but unlikely

Recording of Adverse Events

Adverse events will be recorded for study subjects while they are enrolled in the trial (maximum 2 year enrollment). Serious adverse events that occur at any time after the inclusion of the subject in the study (defined as the time when the subject is randomized) up to 30 days after the subject completed or discontinued the study medication must be reported. The subject is considered to have completed the study either after the completion of the last visit or contact (e.g. phone contact with the investigator or designee), or 30 days after the last dose of the study medication, whichever is later.

As noted above, the incidence of major adverse cardiovascular events (mortality, myocardial infarction, cerebrovascular accident, hospitalization for coronary ischemia, and need for coronary intervention) and bleeding events will be recorded (and noted as adverse events) for trial subjects in the 2 year period after CABG. If, during trial enrollment, a participant develops a major adverse cardiovascular event or major bleeding event, the TARGET blinded study

medication will be discontinued. The participant will then receive open label treatment as indicated by the clinicians involved in the patient's care.

The following variables will be collected for each AE:

- Adverse event description
- The date when the AE started and stopped
- Whether the AE is serious or not
- Investigator causality rating against the study medication
- Action taken with regard to study medication
- Whether AE caused subject's withdrawal from study
- Patient outcome

In addition, the following variables will be collected for SAEs:

- Date AE met criteria for serious AE
- Date investigator became aware of serious AE
- Reason AE is serious (i.e. hospitalization, probable cause of death)
- Dates of hospitalization, discharge, and/or death
- Whether autopsy performed
- Investigator causality rating against the study medication or other medications

Reporting of Serious Adverse Events

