Investigators and other site personnel will inform the FDA, via a MedWatch form, of any serious, *unexpected*, possibly related adverse events that occur in accordance with the reporting obligations of 21 CFR 312.32, and will concurrently forward all such reports to AstraZeneca. A copy of the MedWatch report will be faxed to AstraZeneca at the time the event is reported to the FDA. It is the responsibility of the investigator to compile all necessary information and ensure that the FDA receives a report according to the FDA reporting requirement timelines and to ensure that these reports are also submitted to AstraZeneca at the same time.

When reporting to AstraZeneca, a cover page will accompany the MedWatch form indicating the following:

- Investigator Sponsored Study (ISS)
- The investigator IND number assigned by the FDA
- The investigator's name and address
- The trial title and AstraZeneca ISS reference number

The investigative site will also indicate, either in the SAE report or the cover page, the causality of events in relation to all study medications as determined by the principal investigator.

The SAE report and accompanying cover page will be sent by way of fax to AstraZeneca's designated fax line: [name].

Serious adverse events that do not require expedited reporting to the FDA will be reported to AstraZeneca using the MedDRA coding language for serious adverse events.

All SAEs will be reported to AstraZeneca, whether or not considered causally related to the study drug. All SAEs will be documented.

The investigator will be responsible for informing the institutional review board (IRB) as soon as possible, in accordance with local laws and regulations. All SAEs will be reported to the Western Institutional Review Board (WIRB). The development of serious adverse events that might be attributable to the study medication will lead to the termination of the study drug.

Ethical and Regulatory Requirements

Ethical Conduct of the Study

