Appendix C – Ticagrelor Drug Information

2569300

BRILINTA®
(ticagrelor)
Tablets

HIGHLIGHTS OF PRESCRIBING INFORMATION

These highlights do not include all the information needed to use BRILINTA safely and effectively. See full prescribing information for BRILINTA.

BRILINTA® (ticagrelor) tablets, for oral use

Initial U.S. Approval: 2011

WARNING: BLEEDING RISK

- BRILINTA, like other antiplatelet agents, can cause significant, sometimes fatal bleeding (5.1, 6.1).
- Do not use BRILINTA in patients with active pathological bleeding or a history of intracranial hemorrhage (4.1, 4.2).
- Do not start BRILINTA in patients planned to undergo urgent coronary artery bypass graft surgery (CABG). When possible, discontinue BRILINTA at least 5 days prior to any surgery (5.1).
- Suspect bleeding in any patient who is hypotensive and has recently undergone coronary angiography, percutaneous coronary intervention (PCI), CABG, or other surgical procedures in the setting of BRILINTA (5.1).
- If possible, manage bleeding without discontinuing BRILINTA. Stopping BRILINTA increases the risk of subsequent cardiovascular events (5.5).

WARNING: ASPIRIN DOSE AND BRILINTA EFFECTIVENESS

- Maintenance doses of aspirin above 100 mg reduce the effectiveness of BRILINTA and should be avoided. After any initial dose, use with aspirin 75-100 mg per day (5.2, 14).

DOSAGE AND ADMINISTRATION

- Initiate treatment with 180 mg (two 90 mg tablets) oral loading dose. (2)
- Continue treatment with 90 mg twice daily. (2)
- After the initial loading dose of aspirin (usually 325 mg), use BRILINTA with a daily maintenance dose of aspirin of 75-100 mg. (2)

DOSAGE FORMS AND STRENGTHS

- 90 mg tablets (3)

CONTRAINDICATIONS

- History of intracranial hemorrhage (4.1)
- Active pathological bleeding (4.2)
- Severe hepatic impairment (4.3)
- Hypersensitivity to ticagrelor or any component of the product (4.4)

WARNINGS AND PRECAUTIONS

- Like other antiplatelet agents, BRILINTA increases the risk of bleeding. (5.1)
- In PLATO, use of BRILINTA with maintenance doses of aspirin above 100 mg decreased the effectiveness of BRILINTA. (5.2, 14)
- Moderate Hepatic Impairment: Consider the risks and benefits of treatment, noting the probable increase in exposure to ticagrelor. (5.3)
- Dyspnea: Dyspnea was reported more frequently with BRILINTA than with clopidogrel. Dyspnea resulting from BRILINTA is self-limiting. Rule out other causes. (5.4)

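### Stopping rules for blinded drug differ between sections in trigger, force and permanence, so the two sites may keep different patients on treatment

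*Combined protocol and SAP*

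**What the plan says.** Five sections of the protocol deal with stopping blinded drug after a clinical event.

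- **Restrictions during the Study.** A serious bleed, with a GI bleed leading to admission as the example, ends blinded drug for good. The only other trigger here is a new need for anticoagulation, after which blinded drug is resumed.
- **Discontinuation of Investigational Drug.** The same two triggers. After serious bleeding, "a study subject will permanently discontinue the study medication". Cardiovascular events are not listed.
- **Withdrawal from Study.** "A patient may be withdrawn from study medication at any time by the study doctor or the sponsor without the patient's consent". The examples end with "if the patient has a serious adverse event (GI bleed), or for any other reason".
- **Recording of Adverse Events.** If "a participant develops a major adverse cardiovascular event or major bleeding event, the TARGET blinded study" medication is to be stopped, and the treating clinicians choose open-label treatment. Causality does not matter, and nothing is said about restarting.
- **Reporting of Serious Adverse Events.** "The development of serious adverse events that might be attributable to the study medication will lead to the termination of the study drug".

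The definitions matter too. Exploratory Objectives and Appendix B define major bleeding by disability, loss of vision from intraocular bleeding, or transfusion of at least 2 units, with a life-threatening subclass. Hospitalisation is not a criterion. Minor bleeding is any other bleed that causes study drug to be interrupted. Serious bleeding has no definition beyond the GI example.

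Appendix C attaches the ticagrelor label, whose boxed warning reads "If possible, manage bleeding without discontinuing BRILINTA. Stopping BRILINTA increases the risk of subsequent cardiovascular events (5.5".

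**The concern.** A coordinator who looks up the section headed for discontinuation finds no instruction for a myocardial infarction, a stroke or a coronary intervention. One who looks up the adverse-event section finds a mandatory stop for all three. For a GI bleed, the protocol uses *will*, with permanence, in one section and *may* in the next. No section says which text governs or that the lists add up.

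Three things are at stake. The first is patient safety: the instruction on whether a patient stays on an antiplatelet study drug after a bleed or an ischaemic event should be the same wherever it is read. The second is exposure. A stop leads to open-label treatment chosen by clinicians, so the rule decides who is still on assigned drug at the 1-year CT. The third is a safety outcome, because a bleed that is not major is counted as minor only if drug was interrupted.

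There are two recruiting sites, and under Monitoring of the Study they monitor themselves. The protocol describes no external check that would notice diverging practice.

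**Working it through.** The plan gives no figure on this point, so the check is to take one event at a time through each section.

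| Event | Restrictions; Discontinuation | Recording of AEs | Reporting of SAEs | Withdrawal |
|---|---|---|---|---|
| (a) MI or coronary intervention, judged unrelated to drug | not listed | must stop, permanence not stated | not triggered | may stop |
| (b) GI bleed, hospitalised, 0–1 unit transfused, not disabling, no life-threatening feature | must stop, permanently | not triggered (not a major bleed) | must stop if possibly attributable | may stop |
| (c) Major bleed that is not a hospitalised GI bleed | unclear whether it is *serious* | must stop, permanence not stated | must stop if an SAE and possibly attributable | may stop |
| (d) SAE, neither bleed nor cardiovascular event, possibly attributable | not listed | not triggered | must stop | may stop |

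**Trigger.** No two of the four columns have the same triggers. Event (a) is a mandatory stop in one column only. Events (b) and (c) differ because hospitalisation marks serious bleeding while transfusion or disability marks major bleeding.

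**Force.** Event (b) is mandatory in the first column and discretionary in the last, and the SAE example in Withdrawal from Study is a GI bleed.

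**Permanence.** It is stated only for serious bleeding. Resumption is described only for anticoagulation. For (a) and (c) the protocol states neither.

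**Effect on the bleeding count.** Take event (b) again. It is not major. If drug is stopped, it meets the minor-bleeding definition. If a site relies on the discretionary wording and drug continues uninterrupted, it falls in neither bleeding category, although it is still recorded as an SAE because the patient was hospitalised. The same bleed is counted or not according to the section followed.

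**Effect on the primary analysis.** Under Statistical Analysis, outcomes are compared by intention to treat. Restrictions during the Study keeps patients in follow-up with CT despite drug interruptions (in the anticoagulation paragraph) and keeps patients with serious bleeds in follow-up. None of the stopping texts removes a patient from the primary comparison.

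**The case against.** The best defence is that this is mostly silence and not contradiction. Apart from anticoagulation, no section tells a site to keep or restart blinded drug after one of these events. A site could apply every trigger at once and comply with all sections. The *may* sentence can be read as a general power to withdraw a patient without consent, covering non-compliance and pregnancy as well, which need not weaken a specific *will*. Many bleeds converge too: a hospitalised GI bleed is an SAE, and if it might be attributable the reporting section also ends drug. Since resumption is described only for anticoagulation, no restart elsewhere is a fair inference.

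Much of this stands. The triggers can largely be combined. But the protocol never says that they should be, and combining them still leaves permanence unstated for cardiovascular events and for major bleeds outside the GI example.

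Three stronger readings are tempting and not supported.

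- *The sites will treat patients differently.* This is conditional. Both hold one protocol and, under Training of Study Site Personnel, staff are trained on it.
- *The inconsistency costs power.* Comparing a trial in which some ticagrelor patients stop with one in which none do measures the effect of stopping, not of inconsistency. Sites that differ would lie between two consistent policies, so reconciling the text need not recover any power. Randomisation is stratified by site and treatment is blinded, so a site's practice applies to both arms.
- *The label is a further, conflicting stopping rule.* Appendix C is drug information. Its wording is conditional and addresses acute coronary syndrome with background aspirin, whereas this trial gives ticagrelor without aspirin. It is a tension to acknowledge.

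It is also true that action taken on study medication, and whether the event caused withdrawal, are already collected for each adverse event.

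**Conclusion.** The concern holds as a mismatch between sections that should be reconciled. Depending on the section read, the same event can be a mandatory permanent stop, a mandatory stop of unstated duration, a discretionary stop, or not listed. That bears on patient safety, on how long patients stay on assigned drug, and on the minor-bleeding count.

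Its size cannot be put as a number. The documents give no rate for these events under this regimen: the PLATO CABG figures in the background come from acute coronary syndrome patients on ticagrelor or clopidogrel with aspirin. Nor do they show that practice has diverged.

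The conclusion assumes only that the two sites could rely on different sections, which the protocol does nothing to prevent. It is not a claim that patients leave the primary analysis or that the stated power is reduced. It takes no position on which stopping rule is clinically right.

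**What to change.** Replace the scattered text with one stopping table, used by both sites and cross-referenced from Restrictions during the Study, Discontinuation of Investigational Drug, Withdrawal from Study, Recording of Adverse Events and Reporting of Serious Adverse Events. For each event the table should state:

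- whether stopping is mandatory or discretionary;
- whether it is permanent or may be followed by resumption;
- which single bleeding definition is the trigger.

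A sentence should acknowledge the tension with the label text in Appendix C and say how the investigators resolved it. The choice of rule is theirs.

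On the case report form, extend the existing item on action taken with two fields: date of stop, and permanent or temporary.

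The cost is a wording amendment, which needs ethics board approval and notice to the drug supplier under Changes to the Protocol and Informed Consent Form, and two form fields. No extra patients, visits or procedures are needed.

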All personnel will be properly trained in the protocol and procedures expected of them. In addition, refresher training may be conducted, as needed. Training logs will be kept in the study regulatory binders.

Monitoring of the Study

The sites will perform self monitoring of this study.

Source Data

All source documents will be maintained in the research chart for each subject. In addition, electronic medical records (EMR) may also be utilized by the study facility. It is the practice of the research facility to allow EMR access to monitors or auditors, if requested.

Study Timetable and End of Study

Patient recruitment is expected to be completed within 2 years of initiating the study. Once the final patient has been recruited, follow-up will last for 2 additional years. The study duration is estimated at 4 years.

During the time of enrollment, patients will be seen every three months. This includes the 3 month visit, 6 month visit, 9 month visit, and 12 month visit. At the 12 month visit, patients will be given the opportunity to continue in the study for an additional 12 months. This would include the 15 month visit, 18 month visit, 21 month visit, and 24 month visit.

Data Management

All data will be recorded on preprinted case report forms (CRF) suitable for electronic data capture. The case report forms will be kept in the patient's research chart. The research charts will be stored in a locked, secure location. Data will be entered by qualified personnel at the conclusion of study.

Statistical Methods

Sample Size

This trial will be a pilot study. Outcome estimates will form the basis for assessing the feasibility of designing a future large and definitive trial. One hundred fifty patients in each study arm will be enrolled (300 total patients). Since each patient will receive 2 vein grafts, on average, there will be approximately 300 vein grafts in each group (600 vein grafts total). This sample size will be large enough to detect whether a clinically important difference exists in terms of vein graft patency between the groups, but small enough that subject recruitment can be performed in an expedient manner, likely within the first 24 months of the study.

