This trial will not be designed or powered as a definitive clinical trial. Based on several previously published clinical trials, it is anticipated that 10-20% of vein grafts will be documented as occluded at the 1-year time point after CABG. Should ticagrelor improve graft patency and reduce vein occlusion from 20% to 10%, power calculations suggest that this pilot trial will have 96% power to detect a significant difference ($P<0.05$) between the groups. Alternatively, if ticagrelor were to decrease the occlusion rate from 15% to 10%, the power will be approximately 58%.

Statistical Analysis

All study data will be collected in a blinded fashion during the course of the trial. At 1- and 2-years after surgery, the CT coronary angiograms will be read and interpreted by board-certified radiologists with expertise in cardiac CT imaging. The radiologists will be blinded to study treatment assignment. The data analysis will also be performed in a blinded fashion, with un-blinding at the conclusion of the analysis. Study outcomes will be compared on an intention-to-treat basis according to the randomization study-group assignment. Vein graft occlusion, the primary outcome of the study, will be compared between the two randomization groups using a Fisher's exact test. To account for within-patient correlation and the possibility of multi-graft occlusion within individual patients, vein graft data will also be analyzed using logistic regression fit with generalized estimating equations methods. For secondary outcomes, continuous data will be compared between the two groups using two-sided Student's t tests, two-sample Wilcoxon rank-sum tests, or ANOVA, and a Fisher's exact test will be used for categorical data. Time to major adverse cardiovascular event will be determined for the study groups using the Kaplan-Meier method, and groups will be compared with a log-rank test. In accordance with intention-to-treat analysis, clinical and safety data will be analyzed for all randomized patients in the study. This will include data collected

from subjects who have dropped out of the trial or who refuse postoperative CT coronary angiography (5% expected refusal).

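### The stated 96% / 58% power counts 300 grafts per arm as independent, so for any positive within-patient correlation it is too high for the clustered (GEE) analysis

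*Combined protocol and SAP*

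**What the plan says.** Under Statistical Methods, Sample Size, the unit enrolled is the patient: "One hundred fifty patients in each study arm will be enrolled (300 total patients"). The section then moves to grafts: "Since each patient will receive 2 vein grafts, on average", from which it concludes that "there will be approximately 300 vein grafts in each group (600 vein grafts total"). The power statement follows: should ticagrelor "reduce vein occlusion from 20% to 10%, power calculations suggest that this pilot trial will have 96% power" at P<0.05. The second scenario, 15% vs 10%, is given about 58%. No ICC, design effect or sidedness is stated. The section calls the trial a pilot that is not powered as definitive, but also says the sample suffices to detect a clinically important difference in patency.

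Under Statistical Analysis, graft occlusion is compared with Fisher's exact test. A logistic regression fitted by GEE is added: "To account for within-patient correlation and the possibility of multi-graft occlusion within individual patients". The same section expects 5% of patients to refuse the CT angiogram.

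**The concern.** Patients are randomised, but the power calculation counts grafts. Grafts in one patient share the same surgeon, vein quality, risk factors and drug adherence, and the plan itself allows that they may occlude together. Two positively correlated grafts carry less information than two independent ones, so 300 grafts from 150 patients are worth fewer than 300 independent units. The analysis section recognises this and the sample size section does not. As a result, no power is stated for the one graft-level analysis that respects the unit of randomisation.

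At stake is how the pilot is read. The two power figures support the claim that the sample is large enough, and the pilot's estimates are meant to inform a definitive trial. If the graft-count method were carried over unchanged, the later trial would be too small by the design effect.

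**Working it through.** **Inputs from the documents.** 150 patients per arm, a mean of 2 vein grafts, hence 300 grafts per arm; occlusion 20% vs 10% and 15% vs 10%; alpha 0.05; 5% CT refusal.

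**Inputs assumed.** An ICC of 0.1 to 0.3, with 0.05 as a low case. For the number of grafts per patient, either exactly 2, or 1/2/3/4 grafts in 30/45/20/5% of patients. Eligibility requires only one vein graft, so counts will vary, but this split is illustrative.

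**Step 1: reproduce the stated figures.** Two-proportion z-test with pooled variance under the null, no continuity correction:

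power = Φ{ [ (p1 − p2) − z·√(2p̄(1 − p̄)/n) ] / √( [p1(1 − p1) + p2(1 − p2)]/n ) }

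With n = 300 and one-sided z = 1.645:

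- 20% vs 10%: (0.100 − 1.645 × 0.02915)/0.02887 = 1.80, power 96.4%.
- 15% vs 10%: (0.050 − 1.645 × 0.02700)/0.02693 = 0.21, power 58.2%.

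Both stated figures are matched. Alternatives do not match the pair:

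- Two-sided 5%, 300 independent grafts per arm: 93.1% / 45.7%.
- Two-sided exact Fisher, 300 per arm: 92.0% / 41.1%.
- 150 units (patients) per arm, one-sided: 78.5% / 36.8%.
- At two-sided 5%, the stated figures would need 348 and 409 units per arm, which disagree with each other and with 300.

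**Step 2: design effect.** DE = 1 + (m* − 1) × ICC, with m* = E[m²]/E[m], and effective grafts per arm = grafts/DE.

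- Exactly 2 grafts: m* = 2, DE = 1 + ICC.
- Assumed split: E[m] = 2.0, E[m²] = 0.30×1 + 0.45×4 + 0.20×9 + 0.05×16 = 4.7, m* = 2.35, DE = 1 + 1.35 × ICC.

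**Step 3: clustering alone**, with the one-sided test and 300 grafts per arm held fixed. In each pair the first value is for exactly 2 grafts and the second for the assumed split.

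| ICC | Effective grafts per arm | 20% vs 10% | 15% vs 10% |
|---|---|---|---|
| 0 | 300 | 96.4% | 58.2% |
| 0.05 | 286 / 281 | 95.7 / 95.5% | 56.5 / 55.9% |
| 0.1 | 273 / 264 | 95.0 / 94.4% | 54.8 / 53.7% |
| 0.2 | 250 / 236 | 93.3 / 92.1% | 51.8 / 49.9% |
| 0.3 | 231 / 214 | 91.6 / 89.6% | 49.2 / 46.7% |

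**Step 4: all corrections together**, at two-sided 5% after CT refusal: 0.95 × 150 × 2 = 285 grafts per arm.

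| ICC | 20% vs 10% | 15% vs 10% |
|---|---|---|
| 0 | 91.9% | 43.8% |
| 0.1 | 89.2 / 88.3% | 40.5 / 39.5% |
| 0.2 | 86.5 / 84.5% | 37.7 / 36.0% |
| 0.3 | 83.7 / 80.8% | 35.3 / 33.0% |

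**Step 5: separate the causes**, taken in sequence. For 20% vs 10%: sidedness 96.4 to 93.1 (3.3 points), CT refusal to 91.9 (1.2), clustering at ICC 0.1-0.3 to 89.2-80.8 (2.7-11.1). For 15% vs 10%: sidedness 58.2 to 45.7 (12.5 points), CT refusal to 43.8 (1.9), clustering to 40.5-33.0 (3.3-10.8).

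**Check.** In 20,000 simulated trials per setting (beta-binomial occlusion within patient, independence GEE with robust variance, two-sided 5%, 300 grafts per arm), power agreed with the formula within 1 point, and type I error was 4.6-5.3%.

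**The case against.** Four points can be made for the plan.

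*It is a pilot and says it is not powered as definitive.* This reduces the consequence and is why no extra patients are called for. It does not make the stated figures right, and the same section still relies on the sample being large enough.

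*Fisher's test is the named comparison, and no power is claimed for the GEE.* This is correct as a description. It is also true that clustering barely changes the nominal power of an unadjusted graft-level test. But that test assumes independence too. With exactly 2 grafts, an unadjusted two-sided 5% z-test has actual level 2{1 − Φ(1.96/√(1 + ICC))}, or 6.2%, 7.4% and 8.6% at ICC 0.1, 0.2 and 0.3. Power from a test that does not hold its level is no defence of the design.

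*Most of the gap may be sidedness.* A reader who sees 96% / 58% beside 81-89% / 33-41% might put the whole drop down to clustering. The documents do not support that. For 15% vs 10%, the change from one-sided to two-sided (12.5 points) exceeds the clustering loss anywhere in ICC 0.1-0.3. The one-sided level is itself inferred from the reproduction: the plan says only P<0.05, and its one mention of two-sided testing concerns t tests for secondary outcomes.

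*The ICC is unknown and could be small.* This stands. With a mean of 2 grafts the design effect is modest, and at ICC 0.05 the loss is minor. An unknown ICC calls for a stated range, not an unstated zero.

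**Conclusion.** The concern holds in this form: the stated power rests on independent grafts, the plan's own analysis section expects correlation, and for any positive ICC the GEE analysis has less power than stated. The direction follows from the documents. The size does not, because it depends on an assumed ICC and an assumed spread of graft counts. On the scale that reproduces the plan's figures, ICC 0.1-0.3 costs about 1-7 points for 20% vs 10% (to 90-95%) and about 3-12 points for 15% vs 10% (to 47-55%).

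Two stronger readings should be resisted. One is that the effective sample is only 150 per arm; with exactly 2 grafts per patient that needs an ICC of 1, which nothing in the documents suggests. The other is that the trial is too small and must enrol more; for a declared pilot that already shows a scenario with 58% power, the documents do not support this. It is a correction to stated power that should be made, not a fault that undermines the study.

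**What to change.** In Sample Size:

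- State the sidedness of the test.
- Describe the sample as 300 patients with about 600 correlated grafts.
- Deduct the 5% expected CT refusal, leaving about 285 grafts per arm.
- Replace the two power sentences with power for the GEE analysis over a stated ICC range, giving the design effect 1 + (m* − 1) × ICC and labelling the ICC and graft distribution as assumptions. At two-sided 5% and ICC 0.1-0.3, the text would read about 81-89% for 20% vs 10% and 33-41% for 15% vs 10%.

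In Statistical Analysis, add that the observed within-patient ICC will be reported, so that the definitive trial can be sized from it.

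The cost is a few lines of wording and a less favourable stated power. No patients, procedures or changes in enrolment are needed.
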